## 8.2. Schedule of Assessments

The schedule of assessments for treatment and post-treatment follow-up is shown in Table 4. The schedule of assessments for long-term follow-up is shown in Table 5.

Premature discontinuation procedures are provided in Section 7.3.

Treatment Cycle a				e 1	C	ycle	2	Cycle 3			(	Cycle	4	(	Cycle	5	(Re	bsequ Cycle epeat to 1 y	for		Post-treatment Follow-up		
Weeks	Scree ning	w 1	w 2	w 3	w 4	w 5	w 6	w 7	w 8	w 9	w 10	w 11	w 12	w 13	w 14	w 15	w 16	w 17	w 18	End of Tx a	Safety FU	Disease Assess- ment b	Survi -val FU c
Scheduling window (days) d	-28 to -1 days				-1/ +3			-1/ +3			-1/ +3			-1/ +3			-1/ +3			At time of D/C	30 days ±5 post D/C	Every 8 weeks post D/C for up to 2 years	Every 12 week s for up to 2 years
Pembrolizu- mab		Р			Р			Р			Р			Р			Р						
ALKS 4230		Α			Α			А			Α			Α			Α						
Antipyretics		Х			Х			Х			Х			Х			Х						
										Adn	ninist	rative	Proc	edure	es								
Informed Consent	X e																						
Inclusion/ Exclusion Criteria	X																						
Demographics	X																						
Medical History	X																						
Prior and Concomitant Medications f	X	X			X			X			X			X			X				X		

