# Table 4: Schedule of Assessments and Study Visits (Continued)

Treatment Cycle a		0	ycle	ycle 1		Cycle 2			Cycle 3			Cycle	4	Cycle 5			Subsequent Cycle (Repeat for up to 1 year)				Post-treatment Follow-up		
Weeks	Scree ning	w 1	w 2	w 3	w 4	w 5	w 6	w 7	w 8	w 9	w 10	w 11	w 12	w 13	w 14	w 15	w 16	w 17	w 18	End of Tx a	Safety FU	Disease Assess- ment b	Survi -val FU c
	Laboratory Assessments (Safety Labs) (Continued)																						
CBC with Differential n	Xj	x			Х			х			Х			Х			Х			Х	Xº		
Complete Serum Chemistry Panel n	X j	X			X			X			X			X			X			Х	Xº		
Urinalysis n	Xj	X			Х			Х			X p						Х				X°		
TSH, Cortisol, and ACTH q	Х							х						Х			Х						
	•					•				Eff	icacy	Meas	surem	ents		•							
Tumor Imaging	X r						X s				X s						X s			X b,t		X b	
				•		Tu	mor	Biop	sies/	Arcl	nival '	Fissue	e and	Micr	obiota	a Coll	ectior	1					
Archival or Newly Obtained Tumor Biopsy (for Tumor T-cell Clonality; GEP studies, and Sequencing and TMB analysis)		Xu	X v																				

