- o Unresolved abnormal laboratories that are drug-related AEs should be followed until resolution. Laboratories do not need to be repeated after the end of treatment if laboratories are within normal range.

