# **13.5.** Safety and Tolerability Analyses

Safety will be evaluated based on the occurrence of AEs, vital signs, results of clinical laboratory tests, and ECG findings. Reported AE terms will be coded using the Medical Dictionary for Regulatory Activities (MedDRA®) version 21 preferred terms and system organ classes.

Treatment-emergent AEs (TEAEs) are defined as any AE that begins on or after the first administration of the study drug. Adverse event severity will be graded according to the CTCAE v5.0 and terms recorded on the CRFs will be mapped to preferred terms using the most recent version of the Medical Dictionary for Drug Regulatory Activities (MedDRA).

All AEs will be listed. The incidence of TEAEs will be summarized for each group and overall, by severity, and by relationship to study drug as assessed by the Investigator. The summary tables will include the number and percentage of patients with TEAEs overall, by system organ class, and by preferred terms within each system organ class. Similar tables will be prepared for SAEs, TEAEs leading to discontinuation, as well as additional categories of AEs as defined in the SAP.

Results of clinical laboratory tests will be summarized by visit for the absolute value and for change from baseline. Tables showing the shift from baseline will also be presented.

ECG findings will be listed.

Concomitant medications will be categorized and presented using the World Health Organization Anatomical Therapeutic Chemical (WHO-ATC) drug classification system.

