3.13.4. Clinical Laboratory Parameters

Laboratory parameters will be presented in conventional (ie, US) units. Only scheduled laboratory parameters, as specified in Table 1, will be included in the laboratory results summaries, unless specified otherwise. All laboratory data, including those collected at unscheduled visits, will be included in the listings.

For all quantitative parameters listed in Table 1, the actual value and the change from baseline to each postbaseline visit will be summarized by visit using descriptive statistics. Only data collected as scheduled will be included in the summaries. For each parameter, the mean (+/- SE) at each scheduled visit will be plotted for its actual value and its change from baseline. Data collected at the EOS/ET visit will be included as one time point regardless of subjects' EOS status.

In addition, where applicable, hematology and chemistry laboratory determinations will be categorized according to NCI CTCAE (version 5) grades and shifts from baseline NCI CTCAE grades to maximum and final post-baseline grades will be assessed. The baseline and final grades will be defined respectively as the grade of the last measurement collected prior to the first dose of study drug, and as the last post-baseline measurement collected no more than 30 days after the last dose of study drug.

The maximum NCI CTCAE toxicity grade value will be the value with the highest NCI CTCAE toxicity grade collected after the first dose of study drug and within 30 days following study drug discontinuation. In cases where multiple values are collected on the same day, the maximum grade value will be selected as the value for that day.

The number and percentage of patients with baseline grades versus maximum post-baseline grades of and baseline grades versus final post-baseline grades will be summarized.

Detailed listings of data for subjects experiencing NCI CTCAE grade \geq 3 hematology and chemistry values will be provided. All measurements collected, regardless of the number of days after study drug discontinuation will be included in these listings.

Pregnancy test data will be listed.

Number of subjects who meet protocol defined event of clinical interest criteria (Section 12.1.1 of protocol) as below will be summarized and corresponding listing will be presented.

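### Sampling for Safety Follow-up laboratories depends on the patient's result, yet the SAP does not exclude that visit from its by-visit means and plots

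*Protocol*

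**What the plan says.** **Who is sampled.** Protocol Table 4 (Section 8.2) marks CBC, the "Complete Serum Chemistry Panel" and urinalysis in the Safety Follow-up column, timed at "30 days ±5 post D/C", and attaches footnote o to all three. The footnote has two parts: "Unresolved abnormal laboratories that are drug-related AEs should be followed until resolution", and "Laboratories do not need to be repeated after the end of treatment if laboratories are within normal range". At End of Treatment, CBC and chemistry are marked without the footnote. Urinalysis is not marked there.

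**What is done with the values.** Protocol 13.5 states: "Results of clinical laboratory tests will be summarized by visit for the absolute value and for change from baseline". SAP 3.13.4 adds a figure: "For each parameter, the mean (+/- SE) at each scheduled visit will be plotted for its actual value and its change from baseline". It also states: "Only data collected as scheduled will be included in the summaries". SAP 6.1 takes the scheduled analysis visits from the protocol's schedule, as nominal eCRF visits. SAP 6.3 uses observed laboratory data and imputes nothing. Neither document leaves Safety Follow-up out of the by-visit displays.

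**An unmapped time point.** SAP 3.13.4 also refers to an EOS/ET visit, to be shown as a single time point. Table 4 has an End of Treatment column and a Safety Follow-up column, but none called EOS/ET.

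**The concern.** For CBC and chemistry, the schedule through End of Treatment asks for a sample whatever the previous result. At Safety Follow-up a patient whose values are normal may be skipped, while a patient with an unresolved drug-related abnormality is followed. A mean over the patients who happen to be sampled then estimates something different from the means plotted before it, although the figure shows them as one series.

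Safety and tolerability is a secondary objective and the trial has no control arm, so laboratory trends are read against baseline. The follow-up point is where a reader looks to see whether a laboratory toxicity reverses after treatment stops. If the sampled subset is weighted toward patients who were abnormal, real recovery in the whole population can be hidden.

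**Working it through.** The documents give no expected laboratory values, and the share of normal patients who will be retested is not stated. There is no plan figure to reproduce. Every numerical input below is an assumption chosen to show the range.

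**1. No drug effect.** Standardise a parameter to SD 1. Call it abnormal if z > 1.96 at End of Treatment, upper side only. Let p = 0.025 be the abnormal share and q the share of normal patients retested anyway. Let r(E,F) be the End of Treatment to follow-up correlation (0.3 to 0.9) and r(B,E) the baseline to End of Treatment correlation (0.5 to 0.7).

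- Mean End of Treatment z among those retested: m(q) = (1 − q) × 0.05844 / [p + (1 − p)q], where 0.05844 is the normal density at 1.96.
- Mean actual value at follow-up = r(E,F) × m(q). The true all-patient value is 0.
- Mean change from baseline at follow-up = [r(E,F) − r(B,E)] × m(q). The true value is again 0.

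For q = 0: m = 0.05844 / 0.025 = 2.338.

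- Actual value: 0.3 × 2.338 = 0.70 to 0.9 × 2.338 = 2.10 SD too high.
- Change: (0.3 − 0.7) × 2.338 = −0.94 to (0.9 − 0.5) × 2.338 = +0.94 SD, and 0 when the two correlations are equal.

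For q = 0.25: m = 0.75 × 0.05844 / 0.26875 = 0.163. The actual-value shift is 0.05 to 0.15 SD. For q = 0.5 it is 0.02 to 0.05 SD.

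If abnormality is defined symmetrically on both sides, the selected mean is 0 and there is no mean shift.

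**2. With a drug effect.** Simulation with 2,000,000 draws per scenario, all pairwise correlations of the underlying values 0.5, and a drug effect at End of Treatment averaging 1 SD and varying exponentially between patients. With q = 0, 21.8% of patients are sampled at follow-up. Mean change from baseline at End of Treatment is 1.00 SD.

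| Recovery by follow-up | Plotted change, q = 0 | Plotted change, q = 0.25 | True change, all patients |
|---|---|---|---|
| None | 2.12 | 1.44 | 1.00 |
| Half | 1.06 | 0.72 | 0.50 |
| Full | 0.00 | 0.00 | 0.00 |

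In the half-recovery row with q = 0, the plotted line runs from 1.00 to 1.06 while the true mean falls from 1.00 to 0.50. With full recovery the change is right, but the mean actual value is still 0.44 against a true 0.00.

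**3. A concrete case.** Assume a share s of patients ends treatment at ALT 4.0×ULN and the rest at 0.6×ULN, the normal values stay at 0.6, and only the abnormal patients are sampled later, with a fraction f of their value remaining. End of Treatment mean = 4.0s + 0.6(1 − s). Plotted follow-up mean = 4.0f. True follow-up mean = 4.0fs + 0.6(1 − s).

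| s | End of Treatment | Plotted, f = 0.5 | True, f = 0.5 | Plotted line falls if f is below |
|---|---|---|---|---|
| 10% | 0.94 | 2.00 | 0.74 | 0.94/4.0 = 0.235 |
| 20% | 1.28 | 2.00 | 0.88 | 1.28/4.0 = 0.32 |
| 30% | 1.62 | 2.00 | 1.02 | 1.62/4.0 = 0.405 |

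Whether the plotted line rises or falls depends on recovery. Its level is above the true mean whenever 4.0f > 0.6, that is f > 0.15, for any s. For example, s = 20% and f = 0.25 gives a plotted 1.00, below 1.28, but the true mean is 0.2 × 1.00 + 0.8 × 0.6 = 0.68.

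**The case against.** The strongest reply is that footnote o is a permission. It does not forbid sampling patients with normal values, Table 4 still schedules the panels, and modest retesting of normal patients removes most of the shift. The footnote also does not address abnormal values that are not drug-related AEs. Nor does it say whether one abnormal analyte triggers the whole panel. If it does, the other analytes are not selected on their own value. All of this stands and limits the size. It does not make the point comparable with earlier ones, because retesting is left to site practice.

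A second reply is that SAP 3.13.4 never names Safety Follow-up, and the table and figure shells are in a separate document. That is fair, but SAP 6.1 makes the visit a scheduled one and nothing excludes it. The undefined EOS/ET label adds doubt: it could mean End of Treatment, Safety Follow-up, or a pool of both.

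A third reply is that other outputs protect the reader. Summary statistics show n, all laboratory data are listed, and clinically significant values are recorded as AEs with outcome. The CTCAE maximum-grade and final-grade shift tables use each patient's own values up to 30 days after treatment, so patients normal at End of Treatment stay in them. This makes the problem visible and leaves the shift tables largely sound, but it does not correct the plotted means.

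A reader might also infer that this affects every laboratory parameter. It does not: PT/INR, aPTT, TSH, cortisol and ACTH are not scheduled at Safety Follow-up.

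**Conclusion.** The point holds for the by-visit means, changes and mean ± SE plots of the parameters scheduled under footnote o. Followed as written, the plan can yield a Safety Follow-up mean over a subset selected by result, shown alongside means that were not selected this way.

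For actual values of parameters with a one-sided abnormal direction, the shift is toward abnormal and can mask recovery. Under the stated assumptions it is 0.70 to 2.10 SD with no retesting of normal patients and 0.05 to 0.15 SD with 25% retested. These figures assume selection analyte by analyte; selection by panel would dilute them. For change from baseline, and for parameters abnormal in either direction, the sign is not fixed.

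A reader might conclude that only abnormal patients will be sampled and that the last plotted point must therefore look like toxicity. The documents do not support that: the footnote waives repeats without prohibiting them, the direction depends on recovery and on the correlations, and it is not certain which visit is plotted last. The matter is confined to descriptive safety displays and does not touch the primary endpoint.

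**What to change.** In SAP 3.13.4 and the table shells:

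- End the by-visit means, changes and plots for quantitative CBC and chemistry parameters at End of Treatment.
- For any quantitative urinalysis parameter, end them at the last scheduled on-treatment collection, because urinalysis is not marked at End of Treatment.
- Present Safety Follow-up values in listings and in a resolution table. Its denominator is patients with an unresolved drug-related abnormality at their last on-treatment or End of Treatment sample, counted as resolved, improved, unchanged, worse or not sampled.
- Map the EOS/ET time point to a named Table 4 visit, so that End of Treatment and Safety Follow-up samples are not pooled.

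This needs SAP and shell wording only, with no new samples. The cost is one fewer time point in descriptive safety displays.

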#### Protocol ION-01-ALKS4230

p To be repeated every 2 cycles after Cycle 4.

- q TSH, cortisol, and ACTH should be measured at baseline and every other cycle (every 6 weeks). Cortisol should be measured in the morning.
- r The initial tumor imaging will be performed within 28 days prior to the first dose of study drug. Scans performed as part of routine clinical management are acceptable for use as the screening scan if they are of diagnostic quality and performed within 28 days prior to the first dose of study drug. Local reading (Investigator assessment with site RECIST radiology reading) will be used to determine eligibility and for patient management.
- s The first on-study imaging time point will be performed at 6 weeks (±7 days) after the first dose of study drug, then within 7 days prior to every second cycle, or more frequently if clinically indicated. The same imaging technique should be used in a patient throughout the study. Local reading (Investigator assessment with site RECIST radiology reading) will be used to determine eligibility and for patient management.
- t In patients who discontinue study therapy without confirmed disease progression, a radiologic evaluation should be performed at the time of treatment discontinuation (ie, date of discontinue ± 4-week window). If a previous scan was obtained within 4 weeks prior to the date of discontinuation, then a scan at treatment discontinuation is not mandatory.
- u Baseline tumor tissue from an archival tissue sample or newly obtained core or excisional biopsy (FNA not adequate) from patients with oropharynx cancer must be tested locally for HPV status (if HPV status not known) prior to enrollment. Baseline tumor tissue from a newly obtained sample must also be provided to the CIML for PD-L1 biomarker testing (see Laboratory Manual for additional details). Newly obtained tissue may be obtained up to 42 days prior to treatment initiation, as long as the patient has provided study consent. Detailed instructions for tissue collection, processing, and shipment are provided in the Laboratory Manual. If the patient gives permission for the future use of additional biospecimen materials, then any leftover tissue that would ordinarily be discarded will be stored for future, as-yet-identified testing.
- v The post-treatment (second) biopsy will be performed on the same or similar tumor site during the first cycle of therapy at C1D12, or at any time from C1D8 through C1D19.
- w Fecal swab/storage devices and instructions must be given to the patient; sample collection to be performed at home by patient and returned to clinical research site at the next study visit.
- x Additional information regarding correlative studies is located in Table 16, and additional instructions are provided in the Laboratory Manual.

Patient Group	Imaging	Follow-up	AE Tracking
Patients with SD/PR who continue on Tx, no progression, for up to 1 year	9 weeks post-treatment start (within 7 days prior to Cycle 4), then within 7 days prior to every 3 rd cycle Follow-up: every 12 weeks ±1 week	Safety Follow-up Visit at 30 days after discontinuation Clinic visit every 8 weeks	Until 90 days after discontinuation or 30 days after discontinuation if patient begins new anticancer therapy
Patients who progress on-study before 1 year	Per local standard of care	Safety Follow-up Visit at 30 days after discontinuation or before start of new therapy, if applicable (in- clinic) Safety Follow-up Visit at 90 days after discontinuation (in-clinic preferable, by phone possible) Survival telephone call every 12 weeks for up to 2 years	Until 90 days after discontinuation or 30 days after discontinuation if patient begins new anticancer therapy
Patients who discontinue treatment due to any reason other than progression	Per local standard of care or Investigator clinical judgment	Safety Follow-up Visit at 30 days after discontinuation or before start of new therapy, if applicable Clinic follow-up until toxicity resolves or until death	Until 90 days after discontinuation or 30 days after discontinuation if patient begins new anticancer therapy
Patients who achieve CR on Tx (after at least 24 weeks of Tx + 2 doses post-CR imaging)	After discontinuation of treatment: Follow-up: every 12 weeks ±1 week OR at clinical signs/symptoms of progression	Safety Follow-up Visit at 30 days after discontinuation Clinic visit every 8 weeks	Until 90 days after discontinuation or 30 days after discontinuation if patient begins new anticancer therapy

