#### 8.3.10. Tumor Imaging and Assessment of Disease

For the purposes of this study, baseline scans must be done within 28 days before beginning treatment. In addition to a baseline scan, the first on-study imaging time point will be performed

at 6 weeks ( $\pm$  7 days) after first dose, then within 7 days prior to every second cycle thereafter, or more frequently if clinically indicated while the patient is on study.

Patients whose response converts from PD or SD to PR or from PR to CR will have a confirmatory scan for tumor assessments 6 weeks after the response-defining scan. If the patient continues on study after confirmatory scan, then the patient would receive scan per regular schedule. Thereafter, timing of tumor assessments will depend on whether or not the patient continues with study drug (see Table 5 for additional information).

Accumulating evidence indicates that a minority of patients treated with immunotherapy may derive clinical benefit despite initial evidence of PD. Allowance to continue treatment despite initial radiologic progression takes into account the observation that some patients can have a transient tumor flare in the first few months after the start of immunotherapy but with subsequent disease response. Patients will be permitted to continue on treatment beyond initial RECIST v1.1-defined PD as long as they meet the following criteria:

- Investigator-assessed clinical benefit and no rapid disease progression.
- Patient continues to meet relevant eligibility criteria, as determined by the ION and Alkermes Medical Monitors (or designee) in discussion with the Investigator.
- Stable performance status.
- Patient is tolerating study treatment.
- Treatment beyond progression will not delay an imminent intervention to prevent serious complications of disease progression (eg, CNS metastases).

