The decision to continue treatment beyond initial Investigator-assessed progression should be discussed with the ION and Alkermes Medical Monitors (or designee) and documented in the study records. A follow-up scan should be performed at the next scheduled imaging evaluation 6 weeks later to determine whether there has been a decrease in the tumor size or continued PD. The assessment of clinical benefit should be balanced by clinical judgment as to whether the patient is clinically deteriorating and unlikely to receive any benefit from continued treatment. If the Investigator feels that the patient continues to achieve clinical benefit by continuing treatment, then the patient should remain on the study and continue to receive monitoring according to the Schedule of Assessments (Section 8.2), with consultation from the ION and Alkermes Medical Monitors.

Patients may receive study drug while waiting for confirmation of PD if they are clinically stable as defined by the following criteria:

- Absence of signs and symptoms (including worsening of laboratory values) indicating disease progression
- No decline in ECOG performance status
- Absence of rapid progression of disease
- Absence of progressive tumor at critical anatomical sites (eg, cord compression) requiring urgent alternative medical intervention

Table 7:Tumor Imaging/Assessment for Disease ProgressionDiseaseClinically StableClinically StableClinically Unstable

Disease	Clinically Stable		Clinically Unstable	
assessment by RECISTv1.1	Imaging	Treatment	Imaging	Treatment
1 st radiologic evidence of PD	Repeat imaging at approximately 4 to 6 weeks to confirm PD	May continue study drug at the Investigator's discretion while awaiting confirmatory scan	Repeat imaging at approximately 4 to 6 weeks to confirm PD if possible	Discontinue treatment if alternative therapy is warranted
Repeat scan confirms PD a	No additional imaging required	Discontinue treatment	No additional imaging required	NA
Repeat scan shows SD, PR, or CR	Continue regularly scheduled imaging assessments prior to every 3 rd cycle b	Continue study drug at the Investigator's discretion	Continue regularly scheduled imaging assessments prior to every 3 rd cycle b	May restart study drug if condition has improved and/or clinically stable per Investigator's discretion

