Abbreviations: CR=complete remission; NA=not applicable; PD=progressive disease; PR=partial response; RECIST=Response Evaluation Criteria in Solid Tumors; SD=stable disease.

a Patients who are otherwise clinically stable may be continued on study drug, per Investigator discretion. Even if the patient remains otherwise stable, study drug will be discontinued if tumor burden increases by 25% or more following initial confirmation of progression.

b Tumor imaging/assessment will be performed at baseline, at 9 weeks, and prior to every 3rd cycle.

Response and progression for purpose of publication will be evaluated in this study using the new international criteria proposed by the revised RECIST v1.1 guideline. Changes in the largest diameter (unidimensional measurement) of the tumor lesions and the shortest diameter in the case of malignant lymph nodes will be used in the RECIST criteria.

. Clinicians are

Often with immunotherapy, tumors appear larger before they decrease in size.

encouraged to consider this possibility to avoid stopping potentially effective immunotherapy too soon.

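### Protocol Table 5 row 1 and Table 7 set a 9-week on-treatment scan calendar against the better-supported 6-week calendar of Table 4 and Section 8.3.10, so progression dates and the SAP's missed-scan count are not tied to one schedule

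*Protocol*

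**What the plan says.** **Six-week calendar.** Protocol Table 4, footnote s: "The first on-study imaging time point will be performed at 6 weeks (±7 days) after the first dose of study drug". Section 8.3.10 gives the same first scan, "then within 7 days prior to every second cycle thereafter".

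**Nine-week calendar.** Table 5 row 1 covers patients with SD or PR who continue on treatment without progression. It sets imaging at "9 weeks post-treatment start (within 7 days prior to Cycle 4), then within 7 days prior to every" third cycle. In Table 7, the row for a repeat scan that does not confirm PD reads "Continue regularly scheduled imaging assessments prior to every" third cycle. Its footnote b is worded generally: "Tumor imaging/assessment will be performed at baseline, at 9 weeks, and prior to every" third cycle. Yet the text of Section 8.3.10 just before Table 7 says "A follow-up scan should be performed at the next scheduled imaging evaluation 6 weeks later".

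**Responders.** After the confirmatory scan, Section 8.3.10 says "If the patient continues on study after confirmatory scan, then the patient would receive scan per regular schedule". The next sentence says "Thereafter, timing of tumor assessments will depend on whether or not the patient continues with study drug (see Table 5 for additional information".

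**Where the schedule is used.** SAP 3.11.3 dates PFS and DOR at the first documented progression and TTP at confirmed progression. SAP 3.11.3 and SAP Tables 4 and 5 censor PFS and DOR when PD or death follows two or more missed assessments. The SAP does not say which calendar defines a missed assessment.

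**The concern.** Progression by imaging can be dated only at a scan. If sites follow different tables, PFS, TTP and DOR pool patients examined on different calendars, and the estimates partly reflect which table a site read. The 6-month landmark is exposed because it falls close to a week-27 scan on one calendar and just after a week-24 scan on the other.

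The censoring rule is the second route. It counts scans, not weeks, so the same gap in a patient's record can be an event or a censored time according to the calendar assumed. Without a stated reference schedule, that choice would be made during programming.

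**Working it through.** There is no plan figure to reproduce: the point concerns timing, and the documents give no expected median PFS.

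**1. The calendars.** With 3-week cycles, a scan just before Cycle k falls at about week 3(k − 1). Section 9.1.2 caps treatment at 17 cycles.

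| Calendar | Scan weeks | Before Cycles | Scans |
|---|---|---|---|
| A: Table 4 footnote s and 8.3.10, plain reading | 6, 12, 18, 24, 30, 36, 42, 48 | 3, 5, 7, …, 17 | 8 |
| B: Table 5 row 1, Table 7 footnote b | 9, 18, 27, 36, 45 | 4, 7, 10, 13, 16 | 5 |
| A2: footnote s read with the Table 4 grid (marks at W6, W10, W16) | 6, 9, 15, 21, 27, … | 3, 4, 6, 8, 10, … | – |

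Table 5 row 1 cannot be a later phase for responders. Its first scan (week 9) comes before the earliest confirmatory scan of a week-6 response (6 + 6 = week 12).

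**2. Recording delay.** Assumptions, not from the documents: exponential progression with medians of 8, 12, 16 and 20 weeks, detection only at scheduled scans, no deaths. With L = ln 2 / median and scan spacing d, the mean delay is d / (1 − exp(−L·d)) − 1/L.

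| Median (weeks) | d = 6 | d = 9 | Difference |
|---|---|---|---|
| 8 | 3.26 | 5.08 | 1.82 |
| 12 | 3.17 | 4.89 | 1.72 |
| 16 | 3.13 | 4.79 | 1.66 |
| 20 | 3.10 | 4.73 | 1.63 |

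**3. Estimated PFS.** At landmark t the estimate is exp(−L·s), where s is the last scheduled scan at or before t. At week 26, s = 24 (A), 18 (B), 21 (A2). At week 27, s = 24 (A), 27 (B), 27 (A2). Differences in percentage points:

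| Median (weeks) | B − A, week 26 | B − A, week 27 | B − A2, week 26 | B − A2, week 27 |
|---|---|---|---|---|
| 8 | +8.5 | −2.9 | +4.8 | 0 |
| 12 | +10.4 | −4.0 | +5.6 | 0 |
| 16 | +10.5 | −4.3 | +5.6 | 0 |
| 20 | +10.1 | −4.3 | +5.3 | 0 |

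For example, at a 12-week median and week 26, B gives 35.4% and A gives 25.0%. Averaged over weeks 18 to 36, one full common period of the 6- and 9-week spacings, B − A is +1.7 to +2.3 points.

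If half the patients follow each table, each gap is halved. If 20% of the hazard is exactly dated death, B − A becomes +6.2 to +8.0 at week 26 and −2.2 to −3.4 at week 27. Unscheduled and discontinuation scans would narrow the gaps further; this was not quantified.

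**4. Missed-scan count.** Take a patient whose last progression-free scan is at week 18 and whose next scan, at week 36, shows PD. Both weeks are on calendars A and B, and the gap is 36 − 18 = 18 weeks.
- On B, only week 27 is missed: one scan, so a PFS event at week 36.
- On A, weeks 24 and 30 are missed: two scans, so PFS is censored at week 18.

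The same holds for DOR. The SAP states no such rule for TTP.

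**The case against.** The strongest reply is that the documents already say which schedule governs. Section 8.2 gives the treatment period to Table 4 and long-term follow-up to Table 5. Section 11.1 and SAP 1.3.1 send efficacy scans to Table 4. Section 8.3.10 repeats week 6, and sends patients treated beyond progression to the Section 8.2 schedule. On this view Table 5 row 1 is simply an uncorrected row. That largely stands: a reader might infer two schedules of equal rank, and the documents do not support it. But row 1 is addressed to patients on treatment and timed from treatment start, and Section 8.3.10 points responders to it.

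Second, the Table 7 cell is reached only after a first PD, which has already dated PFS and DOR. This also stands. That cell mainly affects TTP. For PFS and DOR the conflict rests mainly on Table 5 row 1 and the general wording of Table 7 footnote b.

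Third, the week-26 gap tempts a reader to infer a bias of about 10 points in 6-month PFS. The working does not support that: the sign turns at week 27, the average is about 2 points, and the contrast assumes all patients on one calendar against all on the other. Table 5 also allows scans up to 7 days before the cycle, so its week-27 scan may itself fall at the landmark.

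Finally, this is a single-arm study with no between-group PFS comparison specified, and the binary primary endpoint is little affected. That limits the importance of the point but does not remove the contradiction.

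**Conclusion.** The protocol contradicts itself on on-treatment imaging. Table 4 is the better-supported schedule; Table 5 row 1 and Table 7 do not match it, and no text reconciles them. The consequence is confined to secondary endpoints: recorded progression about 1.6 to 1.8 weeks later on the 9-week calendar than on weeks 6, 12, 18…, and about 2 points of estimated PFS on average, with larger swings of either sign at particular landmarks. The sizes rest on the assumed exponential medians, detection at scheduled scans only, and full adherence to one calendar or the other; they shrink if only some sites follow Table 5. No week-52 comparison is offered for the grid reading of footnote s, since it would need a scan before a Cycle 18 that the 17-cycle cap excludes. The dependence of the missed-scan count on the calendar needs none of these assumptions. This should be fixed, but it does not threaten the primary analysis.

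**What to change.** In the protocol:
- Keep the Table 4 / Section 8.3.10 schedule and write it as explicit weeks or cycles, for example weeks 6, 12, 18 and 24 (before Cycles 3, 5, 7 and 9), with the Table 4 grid matched to it.
- Correct Table 5 row 1 and Table 7 (body and footnote b) to the same schedule.
- Limit the Table 5 pointer in Section 8.3.10 to patients off study drug.

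In the SAP:
- State that missed assessments for PFS and DOR are counted against that schedule, with expected scan dates moved when a cycle is delayed (Table 4 footnote a allows delays for toxicity). The count-based rule can stay.
- Correct the reference to Table 1 in SAP 6.1 to protocol Table 4. This is clerical.

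The cost is a text clarification to three protocol tables and one sentence, plus one sentence and one table number in the SAP. No scans are added beyond the Table 4 schedule. The SAP change should be made before database lock.
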